7.2.2.1. Estimand Framework for Secondary Endpoints

The intercurrent events, strategies, and the corresponding missing data handling approaches for the secondary estimands of interest for the secondary endpoints are provided in detail in Table 3:

Table 3: Summary of Estimands for Secondary Endpoints

	Estimand			
Endpoint Category	Endpoint	Population	Intercurrent event(s) handling strategy and missing data handling	Population-level summary
Secondary endpoint - Continuous	Titrated SPT MWD	FAS ¹	If the antihistamines are not withheld before the titrated SPT, the post-randomized data will be assigned by worst observation (including baseline) before the collection of the assessment from the same participant (composite strategy). If all dilutions are missing due to any reason, e.g., early start of BPS, then the averaged value will be imputed using multiple imputation (MI).	ANCOVA model with treatment group and stratification factors as fixed effect and the baseline tSPT as a covariate.
	EEU symptom scores ³ in Part B	FAS-B	Same manner as the primary endpoint with the following exception: If systemic steroids, biologics or immune therapeutics impacting type 2 allergic disease are used due to birch pollen related symptoms ⁶ prior to the EEU challenge, data will be set to mean score from 2 to 6 hours in the baseline EEU (BOCF, composite strategy).	Same manner as the primary endpoint
	Field symptom scores ⁴ in BPS ⁵ and peak BPS	FAS-B	 The intercurrent events will be handled as follows: If Systemic steroids, Biologics or immune therapeutics impacting type 2 allergic disease are used due to birch pollen related symptoms⁶, data will be set to mean score from the other participants in the same treatment group (composite strategy). If due to any other reason, data after the use of medication will be set to missing (hypothetical strategy). Study provided anti-allergy rescue treatment taken during the study: all available data will be utilized (treatment policy) Data during travel periods with no exposure to birch pollen will be set to missing and other observed data during exposure to birch pollen will be used to calculate the mean scores (while on treatment policy) 	ANCOVA model with treatment group, stratification factors as fixed effect, average pollen count during local BPS and the corresponding pre-treatment baseline symptom scores as covariate.

^[1] Endpoints related to tSPT at day 127 will be analyzed in subgroup that had a visit 10 performed at least 12 weeks after Part A dose (not included if visit 10 combined with other visits or if visit 10 done prior to other out-of-season visits).

^[2] Rescue medication may be given during the EEU challenge if any severe or clinically concerning reactions (as judged by the PI).

^[3] EEU symptom scores include TNSS (2 to 6 hours), TOSS (2 to 6 hours), TSS (2 to 6 hours).

^[4] Field symptom scores from e-diary include CSMS [TSS+DMS], TSS [TNSS+TOSS], daily TNSS, daily TOSS, and DMS.

^[5] If there is no protocol defined BPS due to local climactic conditions at any pollen site, then those data will not be included in the calculation for field data.

^[6] Whether the medication is used due to birch pollen related symptoms (considered treatment failure) or not will be adjudicated in a blinded manner.

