The effect of REGN5713-5714-5715 on early phase skin responses following titration skin prick test (SPT) with serial dilutions of birch allergen was observed up to 4 months post-dose, as measured by a significant reduction in the AUC of the SPT mean wheal diameters relative to placebo (placebo-adjusted percent changes relative to the baseline SPT of -72.39%, -65.61%, -77.90%, and -73.56% on study days 8, 29, 57, and 113, respectively). Overall, REGN5713-5714-5715 was well tolerated, with no anaphylaxis or evidence of systemic hypersensitivity observed.

A phase 3, randomized, double-blind, placebo-controlled clinical study (R5713-5714-5715-ALG-2001) in 353 birch-allergic participants has been completed. The primary endpoint, daily Combined Symptom and Medication Score (CSMS [TSS+DMS]), averaged over the duration of birch pollen season, met statistical significance. Numerical improvements were observed in TNSS, Total Ocular Symptom Score (TOSS), Daily Medication Score (DMS), and Total Symptom Score (TSS [TNSS+TOSS]); these improvements were more

pronounced during peak season and for participants dosed ahead of the birch season. Robust suppression of skin prick test to birch (and birch-related allergens) was observed in the overall population. REGN5713-5714-5715 900 mg was well tolerated in this subject population. The majority of TEAEs were mild or moderate in intensity and resolved without sequelae. The incidence of SAEs was low and none were deemed related to REGN5713-5714-5715; there were no deaths or adverse events of special interest (AESIs; no severe or systemic hypersensitivity reactions or severe injection site reactions). No new safety signal was observed and overall, REGN5713-5714-5715 900 mg SC had a favorable safety profile.

Taken together, these clinical studies, during experimental and natural exposure to birch pollen, support the use of REGN5713-5714-5715 in the prevention of allergic symptoms in patients with birch pollen allergy upon exposure to birch pollen. The main purpose of this study is to confirm that a combination of all 3 antibodies is required for maximal treatment effect due to broader epitope coverage when 3 antibodies are utilized together.

Additional background information on the study drug and development program can be found in the Investigator's Brochure.

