2.2. Sample Size and Power Considerations

During the study design stage, a sample size of 65 participants per arm was calculated to obtain 90% power to detect a mean difference in average TNSS (2 to 6 hours) of 1.61 (30% reduction from placebo) between REGN5713-5714-5715 (mean TNSS = 3.74) and placebo (mean TNSS = 5.35), assuming a common standard deviation of 2.8. Assuming 10% dropout, approximately 73 participants per arm will be required to detect a difference of 1.61 in mean TNSS between REGN5713-5714-5715 (3-mAb) and placebo with a minimum detectable difference of 1.0 (~19% reduction from placebo in mean TNSS). Across all 4 treatment arms, the proposed sample size is approximately 300 participants.

This sample size is calculated at a 2-sided significance level of 5% using a 2-sample t-test. Estimates of mean in placebo and variability of the TNSS are based on birch tree SLIT-tablet data (Couroux P, 2019), and a 30% treatment effect relative to placebo is in line with what was observed in the phase 1b POC study for REGN5713-5714-5715.

Pollen related allergy trials are dependent on timing of the specific pollen seasons. As such, enrollment is affected by pollen season start dates. A sample size of 50 participants per arm gives approximately 80% power to detect a mean difference in average TNSS (2 to 6 hours) using the same assumptions. This study is powered to detect differences between REGN5713-5714-5715 900 mg and placebo on the primary endpoint of the mean of TNSS during a birch pollen EEU challenge (2 to 6 hours) at day 29 in Part A.

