8.2. Multiplicity Control

The study is powered on the comparison of the primary endpoint between REGN5713-5714-5715 and placebo for Part A of the study with 2-sided alpha level of 0.05.

A hierarchical procedure will be used to control overall Type-1 error rate at 0.05 for the primary endpoint, TNSS (2-6 hours) in birch challenge EEU at day 29 and change from pre-treatment baseline in titrated SPT mean wheal diameter at day 29 in Part A, for testing multiple comparison groups. Each hypothesis will be formally tested only if the preceding one is significant at the 2-sided 0.05 significance level. The hierarchical testing order is shown as below:

- 1. The mean of Total Nasal Symptom Score [TNSS (2 to 6 hours)] during a birch allergen EEU challenge at day 29, in subjects who receive REGN5713-5714-5715 versus placebo
- 2. The percent change from pre-treatment baseline in birch allergen titrated SPT mean wheal diameter AUC at day 29 in subjects who receive REGN5713-5714-5715 versus placebo
- 3. The percent change from pre-treatment baseline in birch allergen titrated SPT mean wheal diameter AUC at day 29 in subjects who receive REGN5713-5715 versus placebo
- 4. The mean of Total Nasal Symptom Score [TNSS (2 to 6 hours)] during a birch allergen EEU challenge at day 29, in subjects who receive REGN5713-5715 versus placebo
- 5. The percent change from pre-treatment baseline in birch allergen titrated SPT mean wheal diameter AUC at day 29 in subjects who receive REGN5715 versus placebo
- 6. The mean of Total Nasal Symptom Score [TNSS (2 to 6 hours)] during a birch allergen EEU challenge at day 29, in subjects who receive REGN5715 versus placebo

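### The skin-test ANCOVA appears to pool one residual variance over four arms, so steps 3 and 5 are held at 5% only if suppressed arms vary like placebo

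*SAP*

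**What the plan says.** SAP 7.2.2.1, Table 3, gives the model for the titrated skin prick test as an "ANCOVA model with treatment group and stratification factors as fixed effect and the baseline tSPT as a covariate". The population is the FAS, which SAP 3.1 defines as everyone randomized, so all four arms are included.

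SAP 8.2 puts the day 29 percent change in birch wheal AUC into the fixed sequence three times: step 2 (3-mAb versus placebo), step 3 (2-mAb versus placebo) and step 5, worded as "The percent change from pre-treatment baseline in birch allergen titrated SPT mean wheal diameter AUC at day 29 in subjects who receive REGN5715 versus placebo". Each step is tested at two-sided 0.05 and only after the one before it has succeeded.

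Protocol section 1 reports placebo-adjusted percent changes in the same kind of measure for the 3-mAb in the earlier challenge study. All are negative, including the first: "72.39%, -65.61%, -77.90%, and -73.56% on study days 8, 29, 57, and 113, respectively". The day 29 figure is therefore about 66% suppression.

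Neither document mentions arm-specific variances, robust standard errors or a distributional check for this endpoint. SAP Appendix 14.1 lists no supportive analysis for it, and the sensitivity analyses in SAP 7.2.1.2 concern the primary endpoint. The only SD in the plan belongs to TNSS ("assuming a common standard deviation of 2.8", SAP 2.2).

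**The concern.** A single ANCOVA with treatment as a four-level factor uses the average of the four arm variances to judge every pairwise contrast. If no arm differs from placebo, that does little harm. Steps 3 and 5 have to protect a different situation. Step 5 is reached only after both the 3-mAb and the 2-mAb skin-test steps have succeeded, so its null is that 1-mAb equals placebo while two other arms are suppressed. Equal allocation does not cancel the problem, because the two compared arms are only half of those supplying the variance.

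Equal spread is open to doubt here. A wheal cannot be smaller than zero and percent change cannot fall below −100%, so an arm moved a long way towards that floor may well not have placebo's SD. Steps 3 and 5 are the formal skin-test results for the component arms, and Protocol 10.4.3 uses Part A data of this kind to separate the contribution of the antibodies. What is at stake is the error rate of those two steps, or their power, and the coverage of the matching confidence intervals.

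**Working it through.** **The plan's own figure.** SAP 2.2 says that "a sample size of 65 participants per arm was calculated to obtain 90% power". The inputs are a TNSS difference of 1.61, an SD of 2.8 and two-sided 5%. The normal approximation is n = 2 × (1.960 + 1.282)² × 2.8² / 1.61² ≈ 63.6, so 64; the exact t calculation gives 65. Exact-t power is 90.2% at 65 per arm and 81.2% at 50. With 10% dropout, 65 / 0.90 = 72.2, so 73 per arm, and 4 × 73 = 292, or about 300. The figures reproduce. They concern TNSS only; no sample size, SD or power is stated for the skin test.

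**Inputs for the check.** From the documents: four arms at 1:1:1:1, 65 or 50 per arm, two-sided 0.05 at each step. Assumed: the tested arm equals placebo in mean and SD (SD set to 1), and each suppressed arm has SD ratio r to placebo. The range shown is r = 0.34 to 1.5. The lower end is what would follow if scatter shrank in proportion to the remaining response (1 − 0.66 = 0.34).

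**Formula.** At equal n, the actual size of a nominal 5% test with the pooled variance is about 2 × [1 − Φ(1.96 × √V)], where V is the mean of the four arm variances divided by the variance of the compared arms.

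- Step 3 (2-mAb null, only 3-mAb suppressed): V = (3 + r²) / 4.
- Step 5 (1-mAb null, 3-mAb and 2-mAb suppressed): V = (2 + 2r²) / 4.

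For r = 0.5, step 3 has V = 3.25 / 4 = 0.8125, a critical value of 1.96 × 0.901 = 1.767 and size 7.7%. Step 5 has V = 2.5 / 4 = 0.625, a critical value of 1.96 × 0.791 = 1.550 and size 12.1%.

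| r | Step 3 | Step 5 |
|---|---|---|
| 0.34 | 8.4% | 14.3% |
| 0.5 | 7.7% | 12.1% |
| 0.75 | 6.4% | 8.3% |
| 1.0 | 5.0% | 5.0% |
| 1.25 | 3.6% | 2.7% |
| 1.5 | 2.5% | 1.3% |

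**Simulation.** A four-arm ANCOVA with three binary strata and a baseline covariate (6,000 runs per cell, 50 and 65 per arm, normal and complete data) agrees. At r = 0.34, step 3 was 7.8% to 8.4% and step 5 was 13.3% to 13.6%. Over r = 0.34 to 1.25, robust (HC3) standard errors gave 4.3% to 5.3%, and an ANCOVA on the two compared arms gave 4.6% to 5.5%.

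**Effect of the gates.** These are stand-alone sizes. Step 5 also needs steps 1 to 4 to succeed. The whole sequence was simulated at 50 per arm with a 3-mAb TNSS effect of 1.61, SD 2.8, TNSS independent of the skin test, a 2-mAb skin effect of −50, and skin SDs (placebo, 1-mAb, 2-mAb, 3-mAb) of 35/35/25/20, 35/35/20/20 and 40/40/20/20. All but the TNSS figures are assumptions. The chance of a false step 5 claim was about 7% to 9% if the 2-mAb TNSS effect equals that of the 3-mAb, 5% to 6% if it is 1.2, and 4% to 5% if it is 1.0.

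**The case against.** The strongest reply is that nothing in the documents fixes the size or even the sign. No skin-test SD is given, and some of the text points to more spread in the active arms, not less. Table 3 assigns the worst earlier value, baseline included, when antihistamines were not withheld; in a suppressed arm that creates outlying values near zero change. Protocol section 1 reports that, in a mouse model, 90% blockade was reached with plasma from 4 of 5 donors on the 3-mAb but only 1 of 5 on the 2-mAb, which suggests mixed responders. The −65.61% is placebo-adjusted, so the arm's own distance from the floor is unknown. If active arms do vary more, the test is conservative. This stands, and it is why the table runs in both directions.

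The step 5 null is also not very plausible, since REGN5715 is part of both cocktails, and with effects anywhere near the earlier one the choice of variance would not matter. With SDs 40/40/20/20 at 50 per arm, the two methods disagree only for an observed difference of about 12.5 to 15.9 percentage points. That stands too, but controlling the error rate means covering the null whether or not it is likely.

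The dilution by earlier steps is real. It depends on their power, though, and control must also hold when they nearly always succeed.

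Finally, the SAP never states that one variance is fitted to four arms. That is an inference from a plain ANCOVA in the FAS; if pairwise models were intended, saying so would largely settle the point.

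**Conclusion.** This is a cheap improvement, not a demonstrated error. If the ANCOVA pools its variance over four arms, the 5% level at steps 3 and 5 depends on an equal-variance assumption that is unstated, has no planned check, and is open to doubt given about 66% suppression. For assumed SD ratios of 0.5 to 1.5, the stand-alone size runs from 7.7% down to 2.5% at step 3 and from 12.1% down to 1.3% at step 5; only a ratio of 1 gives 5%.

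A reader might infer that the hierarchy's type I error is inflated to 10% or more. The documents do not support that. They give no skin-test SDs, the direction could be conservative, and the overall error is below the stand-alone figure because of the earlier gates. Nor does the point extend to step 2 in the same way: when no arm is suppressed there is no differing variance of this kind to pool.

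**What to change.** For the skin-test contrasts and their confidence intervals, add a sentence to SAP Table 3 or 8.2 prespecifying one of two models:

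- an ANCOVA with arm-specific residual variances (PROC MIXED with REPEATED / GROUP=TRTP and a stated degrees-of-freedom method); or
- a separate ANCOVA for each contrast, using only the two arms compared.

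Make the imputation match. The sample code in SAP 7.2.1.1, written for TNSS, is a single regression with treatment as a main effect, so it draws from one common residual variance. Carried over to the skin test, it would partly undo the change. Imputing within treatment arm, or otherwise allowing arm-specific residual variance, avoids this.

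The two-arm ANCOVA is the version checked by simulation. The GROUP=TRTP model and the imputation step were not simulated and should be tried on mock data first.

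The cost is a SAP sentence, one SAS statement, the adapted imputation and fewer error degrees of freedom. If variances are in fact equal, simulated power at 50 per arm falls from 80.6% to 80.2%, a loss of about 0.4 of a percentage point.

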7.2.1.1. Estimand Framework for the Primary Endpoint

The intercurrent events, strategies, and the corresponding missing data handling approaches for the primary estimands of interest for the primary endpoint are provided in detail in Table 2. Day 29 EEU data during out-of-birch pollen season are planned to assess in the protocol amendment #1 dated November 2022. However, some randomized participants are not eligible to complete EEU Day 29 challenges due to early start of the pollen season. The pollen season occurring before Day 29 is identified as an intercurrent event for the study primary objective. The corresponding estimand framework is used by hypothetical setting not to collect EEU data at Day 29 (all values during EEU Visit 6 are missing). In cases where EEU assessments at Day 29 are collected after the pollen season, these collected EEU data will be set to missing (hypothetical strategy).

Table 2: Summary of Estimand for Primary Endpoint

	Estimand			
Endpoint Category	Endpoint	Population	Intercurrent event(s) handling strategy and missing data handling	Population- level summary
Primary endpoint – Continuous	Mean Total Nasal Symptom Score (TNSS) (2 to 6 hours) in a birch allergen EEU at day 29 in Part A	FAS	 Relevant prohibited medication¹ taken prior to the EEU challenge: all available data will be utilized (treatment policy). Any severe or clinically concerning adverse event necessitating removal from the chamber and/or use of rescue treatment² taken during the EEU challenge: data after exiting the EEU or the use of the rescue medication will be set to mean TNSS from 2 to 6 hours in the baseline EEU (BOCF, composite strategy) In addition, if all values during the EEU visit are missing due to any other reason, e.g., early start of BPS, then the averaged value will be imputed using multiple imputation (MI). 	ANCOVA model with treatment group and stratification factors as fixed effect and the baseline mean TNSS (2 to 6 hours) at visit 2 as a covariate.

^[1] Relevant prohibited medications include allergy relieving medications (treatment policy); no participants used systemic steroids, biologics or immune therapeutics or allergen specific immunotherapy that are expected to impact type 2 allergic disease prior to completion of expected out-of-season EEU visits.

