7.2.2. Analyses of Secondary Endpoints

The secondary continuous efficacy endpoints will be analyzed in a manner similar to that described above (Section 7.2.1.1 Table 2) for the primary efficacy endpoint analysis unless further specified in Table 3. In addition, MI will only be applied for endpoints measured at Day 29.

The proportions of participants achieving different degrees of clinical responses and percent change from pre-treatment baseline in TNSS (2 to 6 hours), TOSS (2 to 6 hours), and TSS (2 to 6 hours) will be compared numerically and graphically using the cumulative distribution function. Participants receiving different combinations of the anti-Bet v 1 antibodies in those receiving

REGN5713-5714-5715, REGN5713-5715, or REGN5715 will be compared with placebo, as well as the comparison between any two active groups. The minimum percent improvement in relevant score will be plotted on the horizontal axis and proportion of participants will be plotted on the vertical axis for each treatment group separately. The AUC of the responder curves derived using the trapezoidal rule will also be calculated as a descriptive summary to compare across different symptom thresholds [as well as including response thresholds such as 30%, 50%, 60%, 75% and 90%], at days 29, 57, and 85 after receiving a single dose of REGN5713-5714-5715, REGN5713-5715, or REGN5715.

The proportions of participants achieving different degrees of change and percent change from pre-treatment baseline in the birch (and related allergens) titrated SPT *mean wheal diameter* AUC will be compared graphically using the cumulative distribution function. The AUC of the responder curves may also be calculated as a descriptive summary to compare across different thresholds [as well as including response threshold such as 30%, 50%, 60%, 75% and 90%] at days 29, 57, 85 in participants receiving REGN5713-5714-5715, REGN5713-5715, or REGN5715.

Subgroups listed in Section 7.2.1.3 might also be applied for secondary endpoints for exploratory analysis. Additional potential sub-group analyses for in-season data:

- Grass sensitization status
- Timing of receipt of dose #2 relative to the local BPS (prior to the season start or after season start), as applicable
- The interval between dose #1 and dose #2 (the cutoff will be decided by the distribution of data, e.g., the median may be used), as applicable

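### SAP Table 3 gives birch-related treatment failures the mean diary score of their own arm and calls this composite; the failure drops out of the outcome and, if any occur, the standard error is slightly too small (minor)

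*SAP*

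**What the plan says.** The field-score row of SAP Table 3 (section 7.2.2.1) covers BPS and peak BPS in FAS-B. Footnote 4 fixes its scope: "Field symptom scores from e-diary include CSMS [TSS+DMS], TSS [TNSS+TOSS], daily TNSS, daily TOSS, and DMS". RQLQ(S) is not listed, so five scores are concerned.

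If systemic steroids, biologics or immune therapeutics are used because of birch symptoms, "data will be set to mean score from the other participants in the same treatment group (composite strategy"). Footnote 6 gives the status of that event: "Whether the medication is used due to birch pollen related symptoms (considered treatment failure) or not will be adjudicated in a blinded manner". The next sentence of the row covers the same drugs taken for another reason: "If due to any other reason, data after the use of medication will be set to missing (hypothetical strategy").

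The other two composite rules in Table 3 use the participant's own data. For the same drugs and the same cause, the Part B EEU row says "data will be set to mean score from 2 to 6 hours in the baseline EEU (BOCF, composite strategy"). The titrated SPT row, for antihistamines not withheld, says the value "will be assigned by worst observation (including baseline) before the collection of the assessment from the same participant (composite strategy").

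The field scores go into one ANCOVA with stratification factors, pollen count and pre-treatment baseline. Section 7.2.2 adds: "In addition, MI will only be applied for endpoints measured at Day 29". Section 14.1 lists no supportive analysis for these scores, and the section 8.2 hierarchy does not include them.

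**The concern.** A composite strategy makes the intercurrent event part of the outcome. Here the participant is declared a treatment failure and then scored as average for the arm. This has three consequences.

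- **The failure leaves the outcome.** The assigned value depends on how well the arm-mates did, so the same failure gets a better score in a better arm. The DMS does not recover it, because it scores only the three supplied rescue medications (SAP 7.1).
- **The standard error is too small.** The filled-in values count as observations but add almost no residual variance. Lifting the day-29 limit on MI would not help by itself, because a value already filled in is never missing.
- **The replaced days are undefined.** The sentence on non-birch use says data after the use of medication. The birch sentence does not say whether it means the whole season or only the days from first use, so two programmers could get different averages.

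At stake is how far the nominal Part B field comparisons can be trusted, if such events occur.

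**Working it through.** **Inputs.** The documents give no SD, effect size or power for the diary scores, so results are in SD units. Arm sizes come from SAP 2.2: 65 per arm (90% power) and 50 per arm (about 80%), both for the primary endpoint. With a difference of 1.61, SD 2.8 and a two-sided 5% t-test, the noncentral t gives n = 65 (power 90.2%) and 81.2% at n = 50, so the plan's figures are reproduced. FAS-B holds only participants given dose #2, so its actual size is unknown. The number of failures per arm, k = 1 to 3, is an assumption.

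**Standard error by hand.** Let f = k/n be the share of each arm set to its own arm mean, whole season replaced, failures random.
- Information comes from n(1−f) participants: true SE ≈ σ√(2/[n(1−f)]).
- Residual variance is diluted to about (1−f)σ² while n is counted in full: model SE ≈ σ√(2(1−f)/n).
- Ratio, model to true: 1−f.
- Type I error ≈ 2Φ(−1.96(1−f)).

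At n = 50: f = 0.02, 0.04, 0.06 gives ratios 0.98, 0.96, 0.94 and 5.5%, 6.0%, 6.5%. At n = 65, k = 1 and 3 gives ratios 0.985 and 0.954, and 5.4% and 6.2%.

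**Standard error by simulation.** Two arms, normal scores with unit SD, assumed correlation 0.4 with baseline and 0.2 with pollen count, strata omitted, ANCOVA, 100,000 trials per type I cell, whole season replaced, k = 1 / 2 / 3 per arm:

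| n per arm | Failures | Model SE ÷ empirical SD | Type I error (%) |
|---|---|---|---|
| 50 | random | 0.975 / 0.959 / 0.937 | 5.5 / 6.0 / 6.5 |
| 50 | worst scorers | 0.952 / 0.914 / 0.876 | 6.2 / 7.2 / 8.4 |
| 65 | random | 0.981 / 0.968 / 0.950 | 5.4 / 5.7 / 6.2 |
| 65 | worst scorers | 0.963 / 0.927 / 0.898 | 5.9 / 6.8 / 7.8 |

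With half the season replaced at 50 per arm: 5.2 to 5.7% (random), 6.0 to 7.5% (worst scorers). With no failures: 5.0 to 5.1%.

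**Estimate.** Let g be the mean gap, in SD, between an arm's failures and its other participants (positive is worse), with subscripts P for placebo and A for active. Under whole-season replacement, observed benefit = rule benefit + f_P·g_P − f_A·g_A. The two differ whenever that product differs by arm. Examples at 50 per arm, rule benefit 0.50:
- 3 failures in each arm, placebo 2 SD worse and active 1 SD worse: 0.50 + 0.06×2 − 0.06×1 = 0.56 observed. The rule understates the benefit although the counts are equal.
- 3 placebo and 1 active failures, each 1 SD better: 0.50 − 0.06 + 0.02 = 0.46 observed. The rule overstates it.

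Conversely, with the observed benefit fixed at 0.50 and failures the worst scorers, simulation gives 0.43 under the rule for 3 placebo and 1 active, and 0.58 for 1 placebo and 3 active. Random failures leave 0.50.

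**The case against.** **Events may be few or absent.** The drugs are prohibited during the study (Protocol 7.9.1), recent biologic use is an exclusion, and rescue medication is supplied. SAP Table 2 footnote 1 reports that "no participants used systemic steroids, biologics or immune therapeutics or allergen specific immunotherapy that are expected to impact type 2 allergic disease" before the expected out-of-season EEU visits were completed. The 1 to 3 per arm has no source in the documents. This stands, and it sets the severity.

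**The contrast with the EEU row is weaker than it looks.** The EEU baseline is a birch challenge in which eligibility required TNSS of at least 6 at two time points, so carrying it forward assigns a bad score. The diary baseline is recommended outside relevant pollen seasons, so carrying it forward could assign a mild one. A different field rule is therefore understandable. That does not justify borrowing the arm-mates' mean and calling it composite.

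**Stronger readings that a reader might infer, and that the documents do not support:**
- *The rule favours active treatment, or always flatters failures.* The direction depends on counts and gaps by arm. Systemic steroids could lower diary scores, and the rule would then raise them.
- *Type I error is 8.4%.* That needs three failures in each arm who are exactly the three worst scorers, with the whole season replaced. It is a stress case.
- *The trial's main conclusion is at risk.* The primary endpoint and the hierarchy do not use these scores.
- *Failures would be hidden.* SAP 9.3 tabulates medications by arm. What is missing is a split by adjudicated birch attribution.

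**Conclusion.** Wrong as written, but minor. The replacement is single own-arm mean imputation, not a composite strategy, and the days it covers are undefined. Its effect is nil with no events.

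Under the assumption of 1 to 3 random failures per arm, 50 per arm and the whole season replaced, the model SE is about 2 to 6% too small and nominal type I error about 5.5 to 6.5%, with about 8.4% as the upper stress case. The effect is smaller at 65 per arm or if only part of the season is replaced. The estimate can move either way relative to the observed-score difference.

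The labelling fault and the undefined window are certain from the text. The numerical size depends on an in-season event rate that the documents do not give.

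**What to change.** In the field-score row of Table 3, stop filling in the own-arm mean and choose one of two rules.

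- **(a) Hypothetical.** Extend the next sentence of the row to birch-related use: data after the use of medication are set to missing, labelled hypothetical. For whole-season loss and random failures this restores the SE without MI (simulated type I error about 4.7 to 5.3%). It does not if failures are the worst scorers (about 6.8% with 3 per arm at 50 per arm).
- **(b) Composite, if a penalty is intended.** Assign a prespecified unfavourable value from the participant's own data, by one rule in all four arms. The price is a larger SE and some power. One version, own worst diary day from first use with half the season replaced (30 diary days, within-person day SD equal to the seasonal SD, both assumed), gave power of 75% (random) or 68% (worst scorers) with 3 failures per arm at 50 per arm, against 78% on observed scores. If one worst CSMS day supplies all components, TNSS or TOSS on that day need not be unfavourable, and the window for peak BPS must be stated.

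Under either rule, state which days are replaced, add one sensitivity analysis on observed scores (treatment policy), and report adjudicated birch-related failures per arm. The cost is one or two sentences and one or two tables, with no new data. It is best settled before Part B data are unblinded.
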